## 5.1.2. Data Handling Rules

As sensitivity analyses, the change in MADRS total score, MADRS-6 total score, HAM-A total score, and PHQ-9 total score will be analyzed using an analysis of covariance (ANCOVA) model, using last observation carried forward (LOCF) data. These analyses are further described in Sections 5.2.3.3, 5.3.4.2, and 5.3.8.2.

For the analyses of response of depressive symptoms based on MADRS total score (Section 5.3.1), remission of depressive symptoms based on MADRS total score (Section 5.3.2), response of anxiety symptoms based on HAM-A total score (Section 5.3.5), and response and remission of depressive symptoms based on PHQ-9 total score (Section 5.3.8.2), both observed case and imputed case where subjects with missing values will be imputed as non-responders/non-remitters will be presented.

For the graphical presentations of the cumulative response rates, defined as the percentage of subjects experiencing at least a given value of percent reduction from baseline to the end of Week 6 for MADRS total score (Section 5.3.1), HAM-A total score (Section 5.3.5), and PHQ-9 total score (Section 5.3.8.2), both observed and LOCF data will be presented. Since ISI is collected at only 1 postbaseline time point, the cumulative response curve for ISI (Section 5.3.3.2) will be presented using observed data.

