## 5.2. Primary Efficacy Endpoint

## 5.2.1. Definition

The primary efficacy endpoint is the change in MADRS total score from baseline to the end of Week 6. The MADRS will be performed by independent, centralized remote raters during the study. The MADRS is a clinician-administered scale designed to measure depression severity and consists of 10 items, each of which is scored from 0 (item not present or normal) to 6 (severe or continuous presence of the symptoms). The MADRS evaluates apparent sadness, reported sadness, inner tension, reduced sleep, reduced appetite, concentration difficulties, lassitude,

inability to feel, pessimistic thoughts, and suicidal thoughts. The recall period for the MADRS is 7 days.

A total score (0 to 60) is calculated by adding the scores of all 10 items. Higher scores represent a more severe condition. Imputation of the total score will be performed only when 1 item score is missing. If 2 or more items are missing, the total score will be left missing. The total score will be imputed by calculating the sum of the scores of the non-missing items and multiplying it by the ratio of the maximum possible number of items (i.e., 10) to the number of non-missing items (i.e., 9).

The MADRS change from baseline at Week 6 is calculated as (MADRS total score at Week 6 – Baseline MADRS total score). Negative changes in MADRS total score indicate improvement.

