## 5.2.3.4. Mediation Analysis

In the mediation analysis framework, natural direct effect can be conceived of as the independent treatment effect on the outcome (i.e., change in MADRS total score) that is above and beyond its effect on the mediator (i.e., change in ISI score); controlled direct effect can be conceived of as the independent treatment effect on the outcome controlling the mediator at a fixed level; and natural indirect effect can be conceived of as a treatment effect on the outcome that is accounted for by its effect on the mediator.

A mediation analysis will be performed to examine the mediating role of improvement in sleep assessed by change from baseline in ISI score on change from baseline in MADRS total score provided that both endpoints demonstrate a statistically difference between at least one dose of JNJ-42847922 and placebo. This analysis will assess the extent to which change in MADRS total score may be mediated by or independent of change in ISI score based on observed data (i.e., data collected at each time point without carrying forward previous values) at the end of Week 6. The analysis will consider both change in MADRS total score and change in ISI score as continuous variables. The calculation of the ISI score is described in Section 5.2.3.5.

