• Simulation-based Counterfactual Approach: this analysis introduced by Imai et.al  obtains the natural direct effect and natural indirect effect using numerical simulations. The approach uses parametric bootstrapping to construct the point estimate and its uncertainty estimates for direct effect and indirect effect from the bootstrap sampling distribution. For each bootstrapped sample, change from baseline in MADRS total score and change from baseline in ISI score will be analyzed. The ANCOVA analysis of change in MADRS total score from baseline will include factors for treatment (placebo and JNJ-42847922 dose groups), region, and baseline insomnia status (present/absent), change from baseline (Day 1, predose) in ISI score, treatment-by-change from baseline in ISI score as a covariate. The ANCOVA analysis of change in ISI score will include factors for treatment (placebo and JNJ-42847922 dose groups), region, and baseline MADRS total score as a covariate. The ANCOVA analysis of change in ISI score will include factors for treatment (placebo and JNJ-42847922 dose groups), region, and baseline MADRS total score as a covariate. The ANCOVA analysis of change in ISI score will include factors for treatment (placebo and JNJ-42847922 dose groups), region, and baseline insomnia status (present/absent), and baseline MADRS total score as a covariate. Estimate of the controlled direct effect will be obtained by plugging in the estimated coefficient values and the mean level of change in ISI score into the analytic expressions.

Since the relationship can be bi-directional, a mediation analysis similar to the above analysis will be performed, to assess the extent to which change in ISI score may be mediated by or independent of change in MADRS total score, based on observed data (i.e., data collected at each time point without carrying forward previous values) at the end of Week 6.

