#### 5.3.10.2. Analysis Methods

Descriptive statistics of the actual values on Baseline, Day 8, Day 22, and Day 42 and the change from baseline to Weeks 2, 4, and 6 will be presented for PROMIS-SD raw score and the T-score by treatment group.

The change from baseline to Day 8, 22, and 42 in the PROMIS-SD raw score and the T-score will be analyzed using the same MMRM as described in Section 5.2.3.1 for the primary efficacy endpoint, with the covariate "baseline MADRS total score" changed to "baseline PROMIS-SD raw score" or "baseline PROMIS-SD T-score", respectively.

Frequency distributions of the PROMIS-SD individual items will be provided at each assessment time point.

In addition, the correlations between baseline ISI score as a continuous variable and change from baseline to the end of Week 6 in the PROMIS-SD raw score and T-score will be evaluated by means of scatter plots and if appropriate, regression analysis.

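### The mediation analysis takes sleep and mood change from the same Week 6 visit with no sensitivity analysis, so it can show sleep mediation where there is none, and the reverse run cannot reveal this

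*SAP*

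**What the plan says.** SAP 5.2.3.4 defines the target in counterfactual terms: the "natural indirect effect can be conceived of as a treatment effect on the outcome that is accounted for by its effect on the mediator". The question posed is how far "change in MADRS total score may be mediated by or independent of change in ISI score based on observed data", with both changes taken at Week 6. The analysis is run "provided that both endpoints demonstrate a statistically difference between at least one dose of JNJ-42847922 and placebo". On method: "The approach uses parametric bootstrapping to construct the point estimate and its uncertainty estimates for direct effect and indirect effect". The MADRS model contains treatment, ISI change, their interaction, region, baseline insomnia status and baseline MADRS. The ISI model contains treatment and the same baseline terms.

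On direction, the section says only: "Since the relationship can be bi-directional, a mediation analysis similar to the above analysis will be performed", again on Week 6 data.

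Three other places matter:
- SAP 5.1.2: "Since ISI is collected at only 1 postbaseline time point". No earlier on-treatment ISI value exists.
- SAP 5.2.1: "The MADRS evaluates apparent sadness, reported sadness, inner tension, reduced sleep, reduced appetite", among other items. The outcome scale therefore contains a sleep item.
- SAP 5.3.10.2: "The change from baseline to Day 8, 22, and 42 in the PROMIS-SD raw score and the T-score will be analyzed". A sleep scale is collected at earlier visits but is not used in the mediation analysis.

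Section 5.2.3.4 states no assumption about unmeasured common causes of ISI and MADRS change, no sensitivity analysis for residual correlation, and no rule for reading the two runs together. It also gives no interval level for the indirect effect.

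**The concern.** An indirect effect estimated this way is the treatment effect on the mediator multiplied by the within-arm slope of outcome on mediator. The slope is causal only if nothing else ties the two changes together after adjustment. Here other ties are likely. Protocol Section 1 notes that disturbed sleep is a diagnostic symptom of MDD, MADRS scores sleep directly, and better mood may itself improve sleep. Any of these gives a non-zero slope without sleep mediating anything. Because both changes come from one visit, the data cannot show which came first.

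Whether the antidepressant effect is separate from the sleep effect is a recurring claim of the programme (protocol Synopsis, 1.1.2, 1.3 and 3.2). This is the SAP's only formal analysis of how much of the effect runs through sleep. As written, it could credit part of a pure mood effect to sleep, or the reverse.

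**Working it through.** **Inputs from the documents.** MADRS difference 4.5, SD 10 (0.45 SD), 280 randomised, 25% dropout (SAP 1.4); 2:1:1 allocation at the start (SAP 1.5). Completers: 280 × 0.75 = 210, taken as 105/52/53.

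**Assumptions.** Residual ISI-MADRS correlation ρ, varied. ISI effect 0.45 SD. A 90% interval, as used elsewhere in the SAP, with 95% also shown. Gate passed when at least one dose has one-sided p<0.05 on each endpoint.

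**The plan's own figure.** The SAP states no figure for the mediation analysis. Its stated power of about 85% is reproduced: 86.2% with 210 completers, 2:1:1 and three candidate models, and 83.5% to 85.3% with 10 mg added under three plausible later splits. The inputs are therefore read correctly.

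**Why the reverse run adds nothing.** Let a_I and a_M be the effects on ISI and MADRS, and s_I and s_M the residual SDs. With no path between the two, and leaving out the interaction:
- forward indirect effect = a_I × ρ × s_M/s_I
- reverse indirect effect = a_M × ρ × s_I/s_M

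The gate selects trials where a_I and a_M are clearly non-zero, so both runs then depend on whether ρ differs from zero. Roughly, SE(ρ) = 1/√210 = 0.069, so ρ = 0.2 lies 0.2/0.069 = 2.9 standard errors from zero and ρ = 0.1 lies 1.4. The assumed shared-cause correlation that brings the indirect effect to zero is ρ itself, in both directions.

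**Size of the false effect.** 0.45 × ρ × 10 = 4.5ρ MADRS points. That is 1.35 at ρ = 0.3 and 2.25 at 0.5; the simulation gave 1.4 and 2.3.

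**Simulation with no path in either direction.** Gate-passing trials, interval excluding zero for at least one dose; the last column requires both runs for the same dose:

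| ρ | forward | reverse | both |
|---|---|---|---|
| 0 | 0.17 | 0.17 | 0.12 |
| 0.1 | 0.44 | 0.41 | 0.32 |
| 0.2 | 0.87 | 0.87 | 0.79 |
| 0.3 | 0.98 | 0.98 | 0.95 |
| 0.5 | 0.99 | 1.00 | 0.98 |

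At ρ = 0 the rate per dose is about 0.09, close to nominal. With 95% intervals the forward rate is 0.07 at ρ = 0, 0.94 at 0.3 and 0.96 at 0.5. With an ISI effect of 0.3 or 0.6 SD, or a linear dose-response, both runs stay at 0.96 to 1.00 for ρ of 0.3 or more (90% interval).

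**Mood drives sleep, no sleep mediation.** The ISI effect is now r × 0.45 SD, so the false share of the MADRS effect is r²: 9%, 25% and 49% at r = 0.3, 0.5 and 0.7. The gate opens in about 33% to 74% of trials over that range. Among those, the forward run is falsely positive in 91%, 98% and 99%. A separate coding of the scheme gave 63%, 97% and 99%, so the figure at 0.3 is the least certain.

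**Can the pair tell opposite truths apart?** Both runs exclude zero, among gate-passing trials:

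| r | mood drives sleep only | sleep drives mood only |
|---|---|---|
| 0.2 | 61% | 61% |
| 0.3 | 94% | 92% |
| 0.5 | 98% | 98% |
| 0.7 | 99% | 99% |

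**Item overlap alone.** With an assumed reduced-sleep item SD of 1.2 to 2.0 and item-ISI correlation of 0.5 to 0.7, ρ runs from 1.2 × 0.5/10 = 0.06 to 2.0 × 0.7/10 = 0.14. Forward rates are 0.27 to 0.58.

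**Would an earlier mediator cure it?** No true mediation, same-visit ρ = 0.5, any dose:

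| shared cause | same visit | earlier mediator | plus earlier MADRS |
|---|---|---|---|
| visit-specific | 1.00 | 0.16 | 0.06 |
| half stable | 0.99 | 0.91 | 0.39 |
| fully stable | 1.00 | 0.97 | 0.64 |

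For the two stable cases, a repeat with Day 22 MADRS in both models gave about 38% to 66%; with it in the outcome model only, 68% to 95%. If sleep acts only within the same visit, the lagged forward run detects it in 5% to 6% of trials.

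**The case against.** The SAP states no null hypothesis, interval level or significance rule for the indirect effect. It sets out to estimate an extent, so the rates above measure a reading rule that is supplied here. That stands, and it is why the point is worded as a clearly non-zero estimate and not as a failed test. The false size, 4.5ρ points, does not depend on any such rule.

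The documents give neither the ISI-MADRS correlation nor an ISI effect size. That also stands. A reader might infer that the analysis always manufactures sleep mediation. It does not: at ρ = 0 the rates are about nominal.

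The analysis is gated, is not a protocol objective or endpoint, and is not in SAP Table 4. Protocol 11.8 calls the trial non-confirmatory. All true, but the gate does not help: it admits the trials in which both effects are clear, and in those any residual correlation shows up as mediation.

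The SAP concedes that the relationship may run both ways and never says that the pair will settle direction. That is fair. Where mood drives sleep, a positive reverse run is even correct. But the plan gives no warning that the pair looks the same under opposite truths.

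A reader might also infer that moving to an earlier sleep measure would identify direction. The last table shows that it does not when a shared cause is stable, and the diagnostic overlap of insomnia and MDD makes a stable cause plausible.

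**Conclusion.** The concern holds in conditional form. With mediator and outcome from one visit and no sensitivity analysis, SAP 5.2.3.4 can report a clearly non-zero sleep-mediated effect when sleep mediates nothing. In gate-passing trials this is likely once the residual correlation is about 0.2 or more, and nearly certain at 0.3 when both endpoints have a 0.45 SD effect. The planned reverse run cannot expose it, because it uses the same association.

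The threshold rests on an assumed correlation, an assumed ISI effect, and a 90% interval that the SAP does not prescribe for this analysis. The documents do not support saying that the plan tests a null of no mediation, that a false result is inevitable, or that a lagged analysis would settle direction. What is at stake is the trial's statement about sleep mediation. The change is worth making because it is cheap.

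**What to change.** In SAP 5.2.3.4:

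1. For both the forward and the reverse run, report the indirect effect over a range of residual correlations, and the value at which it becomes zero.
2. Describe the same-visit pair as association and draw no conclusion on direction from it.
3. Repeat the forward run with MADRS-6 (SAP 5.3.15) as outcome, which removes the sleep item.
4. As a supportive analysis only, add a lagged pair from data already collected: Day 22 PROMIS-SD change to Day 42 MADRS change, and Day 22 MADRS change to Day 42 PROMIS-SD change. Put the Day 22 value of the outcome scale and both baselines in both the mediator and the outcome model, and apply the sensitivity analysis in item 1.
5. State the limits of the lagged pair: it can still show false mediation under a stable shared cause, it has little power for effects within a visit, and it targets a different quantity because the Day 22 adjustment variable is itself affected by treatment.

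The cost is SAP wording and a few more regressions, with no new data. The downside is a more cautious mediation statement.

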## 5.2.3.5. Subgroup Analyses

In addition to the analyses described below, descriptive statistics will be provided for the primary efficacy endpoint (change from baseline to the end of Week 6 in MADRS total score) by the subgroups identified in Section 2.8.

## **Baseline ISI Score**

The ISI has 7 questions, each rated on a 5-point Likert scale ranging from 0 to 4. The total score is calculated as the sum of the 7 items.

The correlation between baseline ISI score as a continuous variable and change from baseline to the end of Week 6 in the MADRS total score will be evaluated by means of a scatter plot and if appropriate, regression analysis.

In addition, subjects will be dichotomized based on their baseline ISI score ( $\geq 15$  versus <15) to evaluate whether there are differences in these subgroups (i.e., evaluating change from baseline to the end of Week 6 in the MADRS total score in subjects with ISI score  $\geq 15$  versus subjects with ISI score <15). Descriptive statistics of the change from baseline to the end of Week 6 in the MADRS total score will be presented by treatment group for these subgroups.

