Definitive GLP studies in pregnant rats and rabbits to evaluate the effects of JNJ-42847922 on embryo-fetal development have been completed. JNJ-42847922 did not induce any developmental alterations (external, visceral, and skeletal) in the fetuses. However, a female rat fertility study suggested a reduction in female fertility. Since it is not known what the relevance of these findings are to a woman's ability to become pregnant after taking JNJ-42847922, no new WOCBP will be included in this study until more is learned about the effect of JNJ-42847922 on female reproduction. WOCBP subjects, who are currently enrolled in this study, may continue study participation following discussion between the subject and the investigator of the new rat fertility study results, if they have a negative pregnancy test, and are using reliable contraception.

Blinding, Control, and Treatment Groups

A placebo control will be used to establish the frequency and magnitude of changes in clinical endpoints that may occur in the absence of active treatment. Randomization will be used to minimize bias in the assignment of subjects to treatment groups, to increase the likelihood that known and unknown subject attributes (eg, demographic and baseline characteristics) are evenly balanced across treatment groups, and to enhance the validity of statistical comparisons across treatment groups. Blinded treatment will be used to reduce potential bias during data collection and evaluation of clinical endpoints.

To test the hypothesis that JNJ-42847922 improves depressive symptoms in subjects with and without significant insomnia, randomization will be stratified and roughly balanced between subjects with a baseline insomnia severity index (ISI) score <15 (subclinical or no clinically significant insomnia) and \geq 15 (moderate to severe insomnia). This distribution will essentially mimic the prevalence of significant insomnia in representative samples of subjects with MDD reported in the literature, where mean ISI scores are reported to be approximately 14 (Kenter 2016⁶⁶: mean ISI score =13.8; SEM 6.3) or 15 (Mason 2014⁶⁷: mean ISI score=14.70; SEM=0.92).

Adaptive Design and Interim Analysis

An adaptive design will be used in order to better characterize the shape of the dose-response curve. At the start of study enrollment, subjects will be randomly assigned in a 2:1:1 ratio to receive 1 of 3 treatments: placebo: JNJ-42847922 20 mg: JNJ-42847922 40 mg.

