5. TREATMENT ALLOCATION AND BLINDING

Treatment Allocation

Procedures for Randomization and Stratification

Central randomization will be implemented in this study. Subjects will be randomly assigned based on a computer-generated randomization schedule prepared before the study by or under the supervision of the sponsor.

At the start of study enrollment, subjects will be randomly assigned in a 2:1:1 ratio to receive 1 of 3 treatments: placebo: JNJ-42847922 20 mg: JNJ-42847922 40 mg.

After the interim analysis, subjects will be randomly assigned to study drug, with the allocation ratio adapted according to the dose-response curve observed at the time of the interim analysis. Subjects will be assigned to receive placebo or one of the JNJ-42847922 doses (potential doses include 10 mg, 20 mg, 40 mg).

The randomization will be balanced by using randomly permuted blocks and will be stratified by region (US, EU, and Japan) and by insomnia status (significant insomnia symptoms [ISI score ≥ 15] at baseline versus no significant insomnia symptoms [ISI score < 15] at baseline). In order to randomize approximately equal proportions of subjects with and without significant insomnia symptoms at baseline, the number randomized in either stratum will be capped at 60% of the planned total sample size.

The interactive web response system (IWRS) will assign a unique treatment code, which will dictate the treatment assignment and matching study drug kit for the subject. The requestor must use his or her own user identification and personal identification number when contacting the IWRS, and will then give the relevant subject details to uniquely identify the subject.

Blinding

To maintain the study blind, the study drug container will have a label containing the study name, study drug number, and reference number. The label will not identify the study drug in the container. However, if it is necessary for a subject's safety, the study blind may be broken and the identity of the study drug ascertained. The study drug number will be entered in the case report form (CRF) when the study drug is dispensed. The study drugs will be identical in appearance and will be packaged in identical containers.

The investigator will not be provided with randomization codes. The codes will be maintained within the IWRS, which has the functionality to allow the investigator to break the blind for an individual subject.

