Any secondary efficacy endpoint which is defined as a change from baseline will be analyzed using the same MMRM as for the primary efficacy endpoint, with the corresponding baseline as a covariate. Frequency distributions will be provided for CGI-S, PGI-S, and for the number of responders and remitters.

The correlation between baseline ISI score as a continuous variable and change from baseline to the end of Week 6 in the MADRS total score will be evaluated by means of a scatter plot and if appropriate, regression analysis. In addition, subjects will be dichotomized based on their baseline ISI score (≥15 versus <15) to evaluate whether there are differences in these subgroups (ie, evaluating change from baseline to the end of Week 6 in the MADRS total score in subjects with ISI score ≥15 versus subjects with ISI score <15). The shift in ISI score category (score 0-7=no clinically significant insomnia; score 8-14=sub-threshold insomnia; score 15-21=moderate insomnia, and score 22-28=clinically severe insomnia) from baseline to the end of Week 6 will be presented.

Subjects will also be dichotomized based on whether they have MDD with anxious distress or MDD without anxious distress to evaluate whether there are differences in these subgroups (ie, evaluating change from baseline to the end of Week 6 in the MADRS total score in subjects with and without anxious distress).

The secondary endpoint analyses will not be controlled for Type I error and nominal p-values will be presented.

The analyses for the other secondary and exploratory efficacy endpoints will be described in the SAP.

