## 2.8. Definition of Subgroups

Descriptive statistics will be provided for the primary efficacy endpoint (change from baseline to the end of Week 6 in MADRS total score) by the following subgroups:

• Baseline ISI score (≥15 versus <15, using the randomization stratification factor as entered into IWRS); this will also be used in the analyses as the baseline insomnia status

- MDD subtype based on SCID-CT (with or without anxious distress based on the Structured Clinical Interview for Diagnostic and Statistical Manual of Mental Disorders-Fifth Edition [DSM-5] Axis I Disorders – Clinical Trials Version [SCID-CT])
- Baseline Ruminative Response Scale (RRS) score (≥median score versus <median score in the full analysis set)
- Sex (male, female, undifferentiated)
- Age group (18-34, 35-54, 55-64, 65-70 years)
- Women of Childbearing Potential (WOCBP) (as determined by Reproductive Tracking CRF page) vs. Men and Women of Non-Childbearing Potential (WONCBP)
- Women of Childbearing Potential vs. Women of Non-Childbearing Potential
- Adults (18-64) male, Elderly ( $\geq$ 65) male, Adults (18-64) female, Elderly ( $\geq$ 65) female
- Region (US, Europe, Japan, as defined in Section 2.6)
- Race
- Ethnicity
- MDD with anxiety based on HAM-A (No/Yes, defined as baseline HAM-A total score <18 versus ≥18)
- Number of antidepressants used in the current episode based on the Massachusetts General Hospital-Antidepressant Treatment Response Questionnaire (MGH-ATRQ; 1, 2, 3 or more)
- Number of major depressive episodes in lifetime, including current episode ( $<3, \geq 3$ )
- Prior medication use of adjunctive antipsychotics based on concomitant medication (Yes/No)
- Prior medication use of adjunctive antipsychotics based on concomitant medication and MGH (Yes/No)
- Prior medication use of benzodiazepines (Yes/No)
- Baseline body mass index (BMI; underweight: <18.5 kg/m^2, normal: 18.5 kg/m^2 to <25 kg/m^2, overweight: 25 kg/m^2 to <30 kg/m^2, obese: ≥30 kg/m^2)
- Functional impairment based on baseline SDS category (not impaired [0-3], mild [4-11], moderate [12-19], marked [20-26] or extreme [27-30]).

Additional subgroup analyses of the primary efficacy endpoint are described in Section 5.2.3.5.

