## 5.2.3.1. MCP-Mod Analysis

The primary efficacy endpoint will be evaluated using the generalized MCP-Mod approach. The MCP-Mod approach provides a method for dose-finding using model-based estimation rather than hypothesis testing via pairwise comparisons. The analysis will be done in two steps.

First, a mixed model for repeated measures (MMRM) analysis of the observed data from the placebo and JNJ-42847922 groups will be used as the method of addressing missing data and to

adjust for important covariates. The MMRM will include region (as defined in Section 2.6), time (scheduled Week), treatment (placebo and JNJ-42847922 dose groups), baseline insomnia status (present/absent), and treatment-by-time interaction as factors and baseline MADRS total score as a covariate. An unstructured variance-covariance matrix will be used for observations clustered by subject. In case of convergence problems, alternative variance-covariance structures will be tried in the following order, with the first structure that converges being used in the analysis: heterogeneous Toeplitz, standard Toeplitz, and AR(1) with separate subject random effect. Subjects in the full analysis set who do not have complete data will still contribute to the estimates at the end of Week 6, but will have less weight in the analysis than those subjects with complete data. The Kenward-Roger method will be used for approximating the denominator degrees of freedom. Based on the MMRM, the least-squares (LS) mean estimates for each JNJ-42847922 dose group and placebo at Week 6 and the corresponding variances will be obtained.

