#### 5.3.4.2. Analysis Methods

Descriptive statistics of the actual values on Baseline, Day 8, Day 22, and Day 42 and the change from baseline to Day 8, 22, and 42 will be presented for HAM-A total score, and HAM-A somatic and psychic factor scores by treatment group.

The change from baseline to Day 8, 22, and 42 in HAM-A total score will be analyzed using the same MMRM as described in Section 5.2.3.1 for the primary efficacy endpoint, with the continuous covariate "baseline MADRS total score" changed to "baseline HAM-A total score".

As a sensitivity analysis, the change in HAM-A total score from baseline to the end of Week 6 will be analyzed using an ANCOVA model, using LOCF data. The derivation of the LOCF values is described in Section 5.2.3.3. The ANCOVA model will include factors for treatment, region, baseline insomnia status (present/absent), and baseline HAM-A total score as a continuous covariate. A 90% CI for the difference in LSMeans and p-value will be calculated based on the contrast test statistic for each JNJ-42847922 dose level.

In addition, a frequency distribution over time of the HAM-A total score categories and HAM-A individual item scores at each time point will be provided by treatment group.

The shift in HAM-A total score category from baseline to each time point will be presented by treatment group.

The correlations between HAM-A total score and MADRS total score will be evaluated using Pearson and Spearman correlation coefficients. These correlations will look at the correlations of the actual values at each time point, as well as the change from baseline. Scatter plots will also be presented.

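### Randomization is stratified by insomnia to study efficacy in each stratum, but the SAP plans no within-stratum difference from placebo with a CI and no treatment-by-insomnia estimate

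*SAP*

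**What the plan says.** Protocol 3.2 gives the reason for the stratification: "To test the hypothesis that JNJ-42847922 improves depressive symptoms in subjects with and without significant insomnia, randomization will be stratified". Protocol 5 protects the balance: "the number randomized in either stratum will be capped at 60% of the planned total sample size". The objectives tables (Protocol 2.1, SAP 1.1) make efficacy versus placebo by ISI stratum a secondary objective. Week 6 MADRS change by stratum is a secondary endpoint there and in SAP Table 4.

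On method, Protocol 11.3 has this rule for a secondary outcome: one "which is defined as a change from baseline will be analyzed using the same MMRM as for the primary efficacy endpoint". A later paragraph of the same section says subjects will be split at ISI 15 to look for differences and names no model.

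SAP 5.2.3.5 (Baseline ISI Score) fills that space, in the two strata, with this: "Descriptive statistics of the change from baseline to the end of Week 6 in the MADRS total score will be presented by treatment group". SAP 2.8 is also descriptive and defines the stratum "using the randomization stratification factor as entered into IWRS". For baseline ISI as a continuous variable, the association with MADRS change "will be evaluated by means of a scatter plot and if appropriate, regression analysis".

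The primary MMRM in SAP 5.2.3.1 has region, time, treatment, "baseline insomnia status (present/absent), and treatment-by-time interaction as factors and baseline MADRS total score as a covariate". Other secondary change scores receive that model; for example, the change "in HAM-A total score will be analyzed using the same MMRM as described in Section 5.2.3.1".

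**The concern.** The objective asks how the drug compares with placebo in each insomnia stratum. That calls for a treatment difference per stratum and, for the comparison of strata, a difference of differences. No planned output supplies either with a measure of uncertainty.

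- The by-arm tables give means.
- The primary MMRM adjusts for insomnia status but assumes one common drug effect.
- The mediation analysis in SAP 5.2.3.4 uses change in ISI rather than baseline ISI, and runs only if both MADRS and ISI separate from placebo.
- The optional regression names no terms. If it were fitted without treatment and treatment-by-ISI, its slope would mix prognosis with effect modification.

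Two things are at stake. Bare stratum means invite a claim about insomnia with no interval attached, in a study meant to inform Phase 3. The regression model could also be chosen after the data are seen.

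**Working it through.** **Plan's own figure.** Inputs from SAP 1.4 and 1.5: 280 randomized, 25% dropout, SD 10, difference 4.5, 1-sided 0.05, initial allocation 2:1:1. I assume 2:1:1 throughout, because allocation after the interim is not fixed in the documents. Evaluable: 280 × 0.75 = 210, that is 105 placebo, 52.5 on 20 mg and 52.5 on 40 mg. The maximum-contrast test with the three SAP candidate models has a critical value of 1.867. Power is 84.1% (linear), 92.5% (Emax) and 81.8% (exponential). The equal-weight average is 258.4 / 3 = 86.1%, against a stated figure of about 85%. The planning inputs reproduce, so I use them below.

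**Formulas.**
- Stratum SE = 10 × √(1/n_placebo + 1/n_active)
- Interaction SE = √(SE₁² + SE₂²)
- 90% half-width = 1.645 × SE
- Interaction power ≈ Φ(4.5/SE − 1.645)

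No gain from covariates or earlier visits is assumed.

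**Equal strata (105 evaluable in each).**
- Pooled active: 52.5 v 52.5. SE = 10 × √(2/52.5) = 1.95; half-width 3.2. Interaction SE = 1.95 × √2 = 2.76; half-width 4.5; power for a 4.5-point interaction about 49%.
- One dose: 26.25 v 52.5. SE = 10 × √(1/52.5 + 1/26.25) = 2.39; half-width 3.9. Interaction SE = 2.39 × √2 = 3.38; half-width 5.6; power about 38%.

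**Across the cap.**

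| Contrast | Split | Stratum half-widths | Interaction SE | Interaction half-width |
|---|---|---|---|---|
| Pooled active | 50:50 | 3.2, 3.2 | 2.76 | 4.5 |
| Pooled active | 60:40 | 2.9, 3.6 | 2.82 | 4.6 |
| One dose | 50:50 | 3.9, 3.9 | 3.38 | 5.6 |
| One dose | 60:40 | 3.6, 4.4 | 3.45 | 5.7 |

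Within-stratum power for 4.5 points at 1-sided 0.05 and equal strata is about 75% pooled and 59% for one dose.

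**Sensitivity to dropout.** The Day 42 window in SAP 2.5 opens at Day 33, so some early-withdrawal visits will count as Week 6 and 210 is conservative. Interaction SE for n = 210 / 240 / 280 is 2.76 / 2.58 / 2.39 pooled and 3.38 / 3.16 / 2.93 for one dose. With all 280, the pooled interaction half-width is still 1.645 × 2.39 = 3.9.

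**If 10 mg is added.** Suppose the last 120 subjects are allocated 1:1:1:1. The 10 mg arm then has 30 × 0.75 / 2 = 11.25 per stratum, against (80 + 30) × 0.75 / 2 = 41.25 on placebo. SE = 10 × √(1/11.25 + 1/41.25) = 3.36; half-width 5.5.

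**The case against.** Protocol 11.3 sends change scores to the MMRM with the matching baseline as covariate, which fits the other scales most naturally, and then treats the ISI strata in a paragraph of their own. An omission is clear; a contradiction between Protocol and SAP is arguable. This stands, and it is why the SAP should say how the rule applies.

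Descriptive or non-MMRM analysis of a secondary change score is not unique to ISI. CGI-S and PGI-S use rank ANCOVA, and EQ-5D-5L and WLQ are descriptive only. True, but none of those is a randomization stratum with a stated hypothesis behind it.

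SAP 1.3 states one null hypothesis, the study is non-confirmatory, and no stratum-level test or power is planned. That justifies nominal p-values. It does not justify leaving a treatment comparison without an estimate and interval.

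The stratum tables are randomized comparisons. If they show N, mean and SD, a reader could derive a crude difference and an approximate CI. That also stands. What would be missing is covariate adjustment, MMRM handling of dropout and any pre-specified output.

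Per-dose intervals are wide, close to the assumed 4.5-point effect in the smaller stratum, and a pooled-active contrast is not otherwise planned for MADRS. A full three-way model with four arms, two strata and three visits has 4 × 2 × 3 = 24 cells, some of them small. Both points are fair. They argue for modest claims and allow a simpler model; they do not favour reporting no interval.

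**Conclusion.** The concern holds. The plan stratifies for this question and names it as a secondary objective, but no planned output gives a stratum-specific difference from placebo with a CI, or a treatment-by-baseline-insomnia estimate.

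The missing stratum estimates would be informative for pooled active and fair for a single dose. The interaction interval would be about as wide as the planned effect or wider, so it should be reported as an estimate and not treated as a test. These sizes rest on SD 10, 25% dropout, 2:1:1 throughout and strata between 50:50 and 60:40.

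This is a worthwhile SAP improvement. It does not touch the validity of the primary analysis.

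**What to change.** In SAP 5.2.3.5:

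1. State how the MMRM rule in Protocol 11.3 applies to the ISI-stratum endpoint.
2. Extend the Section 5.2.3.1 MMRM with treatment-by-stratum, stratum-by-visit and treatment-by-stratum-by-visit terms, using the IWRS stratum from Section 2.8. If cells are too sparse, fit the existing MMRM (without the insomnia term) within each stratum and take the difference of the two estimates.
3. Report each dose, and pooled active, minus placebo at Week 6 with 90% CI in each stratum, plus the interaction contrast with 90% CI. Label all of these nominal.
4. If the continuous-ISI regression is run, pre-specify treatment, baseline ISI, treatment-by-ISI, region and baseline MADRS.
5. Keep the descriptive tables. Consider the same reporting for the anxious-distress endpoint, which has the same descriptive plan but is not a stratification factor.

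The cost is SAP wording and a few model outputs on data already collected; alpha and sample size do not change. The downside is a wide interaction interval, which the report should show and describe as such.
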